#### **Recruitment Methods**

We will be recruiting patients from Northeast Ohio ages 6-17 years with patchy alopecia areata. Subjects will be recruited from the Pediatric Dermatology RBC Zagara Clinic by [name], the Dermatology Clinical Trials Unit Database, and from dermatology provider referrals at University Hospitals practices on main campus, Beachwood, Twinsburg, Independence, Westlake, Cuyahoga Falls, and Concord. Patients identified from the clinical trials database will be approached by a letter of recruitment. We will also perform a Trinetx search of the EMR database to identify potential patients; we will contact the providers for these patients for permission to contact the patients and their parents. If identified by provider referral, the referring provider will inform the patient that a member of our clinical trials research group will contact them. A follow-up phone call will be done under the guidelines outlined in the interview guide. In addition, flyers will be placed in clinical areas and patients and their parents may inquire about joining the study by calling the phone number on the advertisement flyer in our dermatology outpatient clinics. The purpose of the phone interview questions is to pre-screen participants prior to commitment of a screening visit. Clinical trials staff may also pre-screen the EMR during the phone interview to aid with interview guide questions. After the initial prescreening phone call, patients will be asked to come to the clinic to begin the screening visit.

## Setting

The research team recruitment efforts and all research procedures will be performed in the dermatology outpatient clinic at UH RBC Zagara Clinic, University Hospitals Cleveland Medical Center, Bolwell 3100 outpatient dermatology clinic, at the Department of Dermatology Skin Study Center, or at University Hospitals Dermatology, [name].

## **Consent Process**

Subjects will be consented during the screening visit in a private patient room located at UH RBC Zagara Clinic. University Hospitals Cleveland Medical Center, Bolwell 3100, outpatient dermatology clinic, at the Department of Dermatology Skin Study Center, or at University Hospitals Dermatology, [name]. Subjects will initially review the consent document with the study coordinator/study physician. After this initial review, the subjects, will be given the opportunity to review independently, discuss the study with family/friends/etc., and then ask the study team their questions or concerns prior to signing the consent. Subjects can take as much time as they need before deciding to participate or not to participate in the study. To ensure participant understanding of the study, the participant will be asked to explain the study back to the coordinator consenting the subject. To minimize coercion, participants will be given time to review the consent alone before deciding. The study coordinator will explain to the participant that their decision to participate/not participate will not impact their standard/routine clinical care.

## **Study Design**

This is an interventional pilot study assessing the tolerability of needle-free delivery administration of ILTA with the Med-Jet as an alternative to conventional syringe and needle in patients with patchy pediatric alopecia areata. There will be a total of four (4) or five (5) visits necessary for study participation. We hypothesize that the Med-Jet will have acceptable pain tolerability, efficacy, safety, and a positive impact on patient quality of life.

### **Study Procedures**

- Informed Consent
  - An Informed Consent Form (ICF) will be signed by at least one parent or guardian before any study-related assessments are performed. Assent will be elicited when applicable prior to any study-related assessments being performed.

## • Study Visits

There will be four (4) or five (5) visits necessary for study participation:

- If all inclusion criteria are met and no exclusion criteria are met on the same day and the patient and their guardian wish to start the study, the baseline visit and screening visit can be completed on the same day. This will decrease the number of visits from 5 to 4. o
- If the patient has complete hair growth prior to the end of the study, they will complete all remaining visits, but they will not receive injections.
- Visit 1 Screening (within 5 weeks prior to baseline visit or same day, estimated time 1 hour if baseline activities are not performed):
  - We will obtain informed consent, review inclusion/exclusion criteria, obtain medical history (medical conditions, surgeries, alopecia areata history, medications, allergies, social history, and relevant family history), obtain vitals, perform a complete skin exam, efficacy assessments, patientreported pain assessments, and quality of life assessments. A urine pregnancy test will be performed for persons of childbearing potential.
- Visit 2 Baseline (Week 0, estimated time 1.5 hours if not performed the same day as screening):
  - This will be the in-office intervention visit to be scheduled within 4-6 weeks of screening visit. We will review inclusion/exclusion criteria, obtain concomitant medications, adverse events (AE), obtain vitals, perform limited skin examination with efficacy assessment, photograph of target lesions, perform intervention injections per protocol, collect patientreported pain assessments and quality of life assessments. A urine pregnancy test will be performed for persons of childbearing potential.
- Visits 3-5 Follow up study period (Week 4, 8, and 12, estimated time 30 minutes each):
  - A limited skin exam, photographs, review of AEs and concomitant medications, efficacy assessments, QoL assessments and pain assessments will be performed. ILTA will be administered at each visit unless complete regrowth has occurred. A urine pregnancy test will be performed for persons of childbearing potential.

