## Background

Alopecia areata (AA) is a significant medical condition that causes emotional and psychosocial distress as well as reductions in quality of life, especially in the pediatric population [Aldhouse et al 2020; Mostaghimi 2021; Christensen et al 2017]. When limited and patchy, an estimated 80% of those affected will see spontaneous recovery; however, this disease is characterized by frequent remittances and relapses and may progress to more severe disease – alopecia totalis or alopecia universalis (Ito 2012; Barton 2021). Currently, there are no Food and Drug Administration- (FDA) approved treatments for pediatric alopecia areata, and there is a paucity of well-designed, randomized-controlled clinical trials (Meah et al 2020; Barton et al. 2021). Current recommendations, however, support the use of intralesional triamcinolone acetonide (ILTA) in adults (Meah et al 2020, Yee et al 2019), and pediatric patients (Barton et al. 2021; Fernando et al. 2020; Wang et al. 2012).

The use of ILTA in the pediatric population is often limited due to fear of injections and pain [Hordinsky 2015]. A 2002 chart review by Tan et al. demonstrated >50% improvement in 65% of pediatric patients at 12 weeks with use of ILTA, but >10% of patients dropped out of the study due to pain (Tan et al 2002). Current methods for pain mitigation include small gauge needles, cold sprays, distraction, and topical anesthetics, each with their own limitations (Want et al. 2012). Controlling pain is important as it can result in several physiological, psychological, and emotional consequences such as hypoxemia, vasovagal reaction, tachycardia, life-long needle phobia, fear of other procedures, higher levels of pain during other procedures, and possible avoidance of the healthcare system as adults (Ballard et al 2018; Birnie et al 2018). Given limited treatment options for pediatric patients with AA, ameliorating the fear and pain associated with needle-based ILTA is preferable, and the Med-Jet injector may be a device that can do just that. If well-tolerated, well-designed, randomized clinical trials may be feasible in the pediatric population.

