## **Study Timeline**

The following chart lists the standard of care for treatment of patchy pediatric alopecia with ILTA. Each visit can be completed within + 7 days of the target date. Screening and baseline visits can be completed on the same day if appropriate.

	Screening	Baseline	5	Study Perio	d
Visit	V1	V2	V3	V4	V5
Week	-4-0	0	4	8	12
Estimated time requirement of visit	1 hour	1.5 hour	30 min	30 min	30 min
Informed Consent	X				
Inclusion/Exclusion Criteria	X	х			
Demographic Data	X				
Past medical and surgical history	X				
Alopecia Areata History	X				
Medications	X				
Allergies	X				
Vital signs (plus height and weight)	X	Х			
Full Skin Examination	X				
Limited Skin Examination		Х	X	X	X
Laboratory assessments	_				
Urine pregnancy test*	X	Х	X	X	Х
Intralesional triamcinolone acetonide		Х	X	X	Х
Photographs		X	X	X	Х
Adverse events		X	X	X	Х
Concomitant medications	_	х	X	X	Х
Efficacy Assessment	X	Х	X	X	Х
Pain Assessment		Х	X	X	Х
Quality of Life Assessments		Х	X	X	X
Patient Survey	· · · · · · · · · · · · · · · · · · ·	X	X	X	X

\*Required for all persons of childbearing potential at each visit.

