## **Risks to Research Participants**

## • Intralesional Injections

- Injections with the Med-Jet Discomfort, bruising, injection site reaction (redness, swelling, pain), and infection
- Skin evaluations
  - Minimal emotional discomfort and embarrassment can be considered a risk
- Questionnaires
  - Minimal emotional discomfort can be considered a risk
- Breach of Confidentiality
  - Study participant information collected in the research process may include; contact information, consent documentation, demographics, social security number (necessary for reimbursement), and personal medical history. All data will be stored on the secure UH or REDCap© server, or as paper records stored in a locked cabinet. Data collected in this study will include: Patient records collected electronically and on paper, consent forms, and urine samples. While we maximize our ability to secure private information, participants could potentially be at risk for anticipated problems such as:
    - Lost or stolen laptops/cabinets storing participant information
    - Faxes sent to the wrong fax machine outside of the Health Sciences Center
    - Paper without PHI not disposed of properly i.e. shredded
    - Information delivered to the wrong participant using the postal service, courier, or other delivery method

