- The PI will ensure protocol adherence, proper protocol conduct, data quality, and subject safety and efficacy by conducting regular meetings with the entire study staff. The adverse events submitted by subject phone inquiry or email will be reviewed and adjudicated with all research team members. In addition, any adverse events or deviations to the protocol or other issues will be discussed at the Regulatory Meeting held monthly in the department of Dermatology.
- **Tissue Samples:** No tissue samples will be taken in this study.
- **Photographs:** All photographs will be de-identified and stored on the secure UH server, only accessible to authorized study personnel. In the event a photograph is taken of the face or any other identifiable feature, the patient's identity may become known.
- Data Transfer/Transmission: Research data will be sent to a statistician for data management after finishing this research study: however, all the data will be stripped of patient identifiers prior to transfer. In order to comply with federal regulations, records identifying participants in this study may be reviewed by authorized study personnel, authorized representatives of the Institutional Review Board, or other federal regulatory officials responsible for oversight of human subject protection. Any data linking participants to their sample will be deidentified. A code will be used to link participants to identifying information and only the investigators and the research study coordinators will have access to this information, which will be stored on a server at University Hospitals Case Medical Center with a separate encryption code. Upon enrollment, each patient record will be stripped of all identifying information and assigned a unique numerical identifier that has no reference to any identifiable patient information.

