In addition, any serious adverse event (grade 3 or greater), except for those reported in the protocol, must be reported to the sponsor by the investigator by telephone, fax or email within 24 hours. A

notification form will then be sent to the sponsor by fax or email with acknowledgement of receipt within 48 hours of the event.

The investigator will also inform the sponsor of adverse events and abnormal results of the analysis, which are defined as decisive for the evaluation of safety of persons taking part in biomedical research.

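### Adverse events are actively asked about only at visits about four weeks apart, with no planned contact after a Week 12 injection, so short-lived site reactions would be under-counted

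*Combined protocol and SAP*

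**What the plan says.** **Scheduled collection.** Under Study Visits, the follow-up entry reads "Visits 3-5 Follow up study period (Week 4, 8, and 12, estimated time 30 minutes each", and at those visits "A limited skin exam, photographs, review of AEs and concomitant medications, efficacy assessments, QoL assessments and pain assessments will be performed". AEs are also listed at baseline. The Study Timeline table marks AEs at baseline and Visits 3 to 5 and nowhere else. Of the visit dates it says "Each visit can be completed within + 7 days of the target date". Injections are given at baseline and at each follow-up visit, including Week 12, unless hair has fully regrown. Week 12 is the last visit.

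**Between visits.** The privacy section says "The adverse events submitted by subject phone inquiry or email will be reviewed and adjudicated with all research team members". The safety monitoring section adds an AE review at each visit and weekly with the principal investigator. No diary, planned call or observation period is described.

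**Timing within a visit.** Pain Score Assessment has pain rated before and after the procedure. Quality of Life Assessment puts its questionnaires before the injection. No such rule is given for AEs.

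**Expected reactions.** Risks to Research Participants lists, for the Med-Jet, "Discomfort, bruising, injection site reaction (redness, swelling, pain), and infection".

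**Sponsor reporting.** For events of grade 3 or higher, apart from those the protocol already reports, the safety monitoring section asks for a report within 24 hours, with no stated starting point. After that a "notification form will then be sent to the sponsor by fax or email with acknowledgement of receipt within 48 hours of the event".

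**The concern.** Several of the named reactions, such as bruising, redness and swelling, can appear and clear between two visits. A child or parent asked about them about four weeks later must recall something minor that has gone. The phone and email route does not close this gap, because families are least likely to volunteer a small bruise. After the last possible injection nobody is scheduled to ask at all.

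Study Design hypothesises that the device will be acceptably safe as well as tolerable, and Potential Benefit to Research Participants hopes to show that needle-free delivery can be used safely. Missed reactions push the results towards that conclusion. The study is small and the device is not FDA-approved, so its site-reaction rate is likely to be carried into the planning of later trials.

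The 48-hour form raises a separate drafting problem. A deadline counted from the event depends on when the family makes contact, which the site does not control.

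**Working it through.** The plan gives no figure of its own on this point, so there is nothing to reproduce. The check is date arithmetic.

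**Inputs from the documents:** visits at days 0, 28, 56 and 84 (Study Visits); a 7-day window (Study Timeline); 15 subjects (Number of Research Participants); up to 4 injection sessions each; 48 hours = 2 days (safety monitoring section). The window prints as plus 7 and may be a misread plus-or-minus sign, so both readings are shown.

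**1. Gap from an injection to the next planned AE question**

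| Reading of window | Baseline to Week 4 | Between later visits |
|---|---|---|
| On target | 28 days | 28 days |
| +7 | 28 to 28+7 = 35 | 56−35 = 21 to 63−28 = 35 |
| ±7 | 28−7 = 21 to 28+7 = 35 | 49−35 = 14 to 63−21 = 42 |

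**2. Age of a reaction when first asked about.** A reaction that starts on days 0 to 3 is raised 28−3 = 25 to 28 days later on the nominal schedule. Assume instead that it starts on the injection day and lasts 3 to 14 days; the documents give no duration. It has then been gone for 28−14 = 14 to 28−3 = 25 days. With +7 the range is 21−14 = 7 to 35−3 = 32 days, and with ±7 it is 14−14 = 0 to 42−3 = 39 days.

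**3. Sessions with no later AE contact.** At most 15 × 4 = 60 sessions take place, of which 15 × 1 = 15 are at Week 12: 15/60 = 25%. Complete regrowth before Week 12 would lower these counts.

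**4. The 48-hour form.** Suppose visits were the only route and onset were uniform over the gap (assumption). The share of events falling within 48 hours before a visit is 2/gap:
- 28 days: 2/28 = 7.1%
- 14 days: 2/14 = 14.3%
- 42 days: 2/42 = 4.8%

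For onset on days 0 to 3, among events not seen by staff at the session, the share is nil even with the shortest gap, because 14−3 = 11 days exceeds 2.

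Now let a share s of qualifying events be phoned or emailed in promptly (assumption). The share able to meet the deadline is s + (1−s) × 2/28:
- s = 25%: 0.25 + 0.75 × 0.0714 = 30%
- s = 50%: 0.50 + 0.50 × 0.0714 = 54%
- s = 75%: 0.75 + 0.25 × 0.0714 = 77%

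As an illustration, a qualifying event on day 5 that is first learned of on day 28 is 28−5 = 23 days old, or 23−2 = 21 days past the deadline.

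**The case against.** The strongest case against has four parts.

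- **Other routes exist.** Families can phone or email, the team reviews AEs weekly, and a Patient Survey is given at each visit. The first of these is a genuine route, so AEs are not captured only at visits. It is passive, though. The weekly review is a team meeting that can consider only what has been reported, and the survey covers tolerability, comfort, fear and preference, not site reactions.
- **The primary objective is not touched.** It is patient-reported tolerability, and pain is rated straight after the procedure. This stands. The point concerns the AE record, and safety is named in the hypothesis but not among the objectives.
- **Order within the visit is not fixed.** Because Study Visits lists AE review before the injection, a reader might infer that it must happen first. The documents do not support that. The same text lists the pregnancy test after the injection, lists pain at Visits 3 to 5 before it although pain is rated on both sides, and the Study Timeline table puts the injection row above photographs and AEs. All that can be said is that no post-injection AE check is specified.
- **The 48-hour rule is narrower than it looks.** It covers only grade 3 or higher and carries an exception for events the protocol already reports, which may include the listed infection and site reactions. A parent is likely to call about an event that needs medical attention. This stands too: ordinary bruises are not on this clock.

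**Conclusion.** The point holds as a gap in ascertainment. Planned AE questioning comes 28 days after an injection (21 to 35, or 14 to 42, by reading of the window), and up to 25% of sessions have no later planned question. The direction is towards fewer recorded reactions, which favours the safety hypothesis. The number missed cannot be derived from the documents. For scale, with 15 subjects each subject whose only reaction goes unrecorded moves a subject-level rate by 1/15 = 6.7 percentage points.

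A reader might infer that the 48-hour deadline cannot be met, or that it would be breached by design. Neither follows: it can be met when staff witness the event, when it starts shortly before a visit, or when the family calls promptly. What holds is that it is not assured for an event first learned of at a later visit, and that the 24-hour clock has no start.

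A reader might also infer, from the mention of "hypoxemia, vasovagal reaction, tachycardia" in Background, that vital signs are needed after each injection, or, from the wording of grade 0, that bruises would be scored as no event. Background describes consequences of pain in general, and the grade 1 definition already fits a mild untreated bruise, so the documents establish neither.

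The conclusion assumes that at least some reactions clear between visits and are not volunteered. It also assumes that no AE contact rule exists elsewhere: Safety Assessments points to a section 6, but no section so numbered appears in the text available, and the safety monitoring section contains no such rule. The changes are worth making, although the primary pain outcome does not depend on them.

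**What to change.** 1. In Study Visits and the Study Timeline table, add an AE and site-reaction question and a site check at the time of the existing post-procedure pain rating.
2. Send parents one brief automated REDCap survey within about a week of every session, including Week 12, asking about the reactions the protocol lists. The system is already described in the privacy section.
3. In the safety monitoring section, start both the 24-hour and the 48-hour clocks when the site becomes aware of the event. State whether the reactions listed under Risks to Research Participants fall under the exception for events the protocol already reports.

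The cost is one short form, a few minutes per visit, edits to the table and text, and no extra visits. One survey per session means at most 60 surveys, and existing staff must check the replies. Reported site-reaction rates will look higher than under the present plan.

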## Inclusion/Exclusion Criteria

Subjects must meet all inclusion criteria and must not meet any exclusion criteria to qualify for participation in the study. The subject's source documents must support his/her qualifications for the study.

## **Past Medical History and Surgical History**

All medical, surgical, and social history, as defined in the electronic Case Report Form (eCRF) Completion Guidelines and the Study Manual, will be recorded. The date of medical diagnoses and surgical procedures will be recorded.

## **Prior and Concomitant Medications and Therapies**

All medications and therapies being taken/used by the subject at the time of consent or at any time during the study will be recorded. All medications and therapies for alopecia areata, will be recorded. The stop dates and reason for stopping all medications and therapies prohibited in the study will be recorded.

- Intervention
  - At least two patches; each measuring 2 cm2 and at least 1 cm from one another will be identified, mapped out, and photographed.
  - Only one of the alopecic patches will be treated.
  - The concentration of ILTA will be controlled at up to 1 mg per cubic centimeter (0.1 ml
     @ a maximum concentration of 10mg/ml) injected every 1 cm until patch has been fully treated. The researcher providing treatment will be properly trained to deliver intradermal injections using the syringe and needle-free system.
  - Med-Jet with Triamcinolone (TAC) Procedure ILTA will be administered into the patches. The PI and co-investigators will be performing interventions and follow proper training by the manufacturer on operation and handling of the device. Training will consist of a live course with a designated manufacturer technician supplemented with training videos. A standard sterile disposable 5 ml syringe will be used to draw TAC using standard sterile protocol. This syringe will be attached to the Med-Jet along with a sterile barrel and disposable sterile tip. The target lesion will be wiped with alcohol and injected with up to 10mg/ml of TAC directed towards the dermis to create a blanching wheal that is 1 cubic centimeter (total of 0.1 ml of injected fluid). The optimal injection pressure used on the subject will start at 130 pounds per square inch (psi) and increased by 5 psi until a blanching wheal is observed. The optimal pressure until the targeted patch is completely treated.
  - Patients will be treated at each visit unless complete regrowth has occurred.
     Photographs will be taken at each visit and activities will be completed as above.

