#### **Clinical Assessments**

- Physician Efficacy Assessments
  - Severity of Alopecia Tool (SALT) Score The SALT score is a visual tool to help assess percentage of hair loss on the scalp. The scalp is divided into four sections top, back, right side, and left side. Each section contributes to a total of 100% (i.e. top = 40%, back = 24%, sides = 18% each). Raters assess total percentage of hair loss in the section and then multiple is by the respective multiplier which is based on that sections total percentage of the scalp 40%, 24%, or 18%. Only terminal hairs are considered hair growth in this tool. (Olsen et al. 2004) Figure 1 illustrates the visual aid and allows for intuitive use. This is a static tool and only quantifies the hair loss at one point in time.
  - Alopecia Areata Investigator Global Assessment (AA-IGA) The AA-IGA categorizes the scalp hair loss into 5 categories based on the SALT score. The five categories are: 1 = None, 2 = Limited, 3 = Moderate, 4 = Severe, and 5 = Very Severe. The corresponding SALT scores for each category are: 1 = 0%, 2 = 1-20%, 3 = 21-49%, 4 = 50-94%, and 5 = > 95%. This is a static tool and only quantifies the hair loss at one point in time (Olsen 2004).
  - "Rule of Thumb" Assessment and Regrowth Categorization A patient's thumbprint projection is approximately 1% of the scalp surface area (King 2019). When selecting the alopecic patch for treatment and its comparator, thumb projections will be used to quantify the percentage of total scalp hair loss contributed by each these patches at baseline. At each subsequent visit, the thumbprint projection from baseline will be used to determine percent of regrowth since baseline. Based on regrowth, the patient will be categorized into one of 6 categories: A0-5. Where A0 = no change or further loss, A1 = 1-24% regrowth, A2 = 25-49% regrowth, A3 = 50-74% regrowth, A4 = 75-99% regrowth, and A5 = 100% regrowth.
- Patient-Reported Efficacy Assessments
  - Patient-Reported Hair Loss Whole Scalp This assessment will apply to the subject's whole scalp surface area. This question will be asked at every visit. And it will include 5 numerical categories: 0 = No missing hair (0% of my scalp is missing hair; I have a full head of hair); 1 = limited area (1% to 20% of my scalp is missing hair); 2 = moderate area (21% to 49% of my scalp is missing hair); 3 = large area (50% to 94% of my scalp is missing hair); and 4 = Nearly all or all (95% to 100% of my scalp is missing hair).

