  - 5-Point Patient-Reported Regrowth Whole Scalp and Selected Patches At each visit after the baseline visit, the subject will be asked about their perceived amount of hair regrowth both for the whole scalp and those patches selected at baseline. The subject will be able to select one of 5 categories: 1 = Further Loss, 2 = No Change, 3 = A Little Improved (<50% regrowth), 4= A lot of improvement (50-99% regrowth), and 5= Complete Regrowth (100%).

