## Data Analysis Plan

Statistical analyses will be completed under the supervision of a statistician. Statistical analysis will be done by statistical software (e.g. SPSS, SAS, R, Excel; etc.) AUROC will be calculated in order to assess for accuracy. The  $\chi^2$  test may be used for comparison of dichotomous variables, and the Mann-Whitney test may be used for non-normally distributed continuous variables. The cutoff value for significance was set at p = 0.05.

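### The plan states no rule for choosing which patch is treated, so its only concurrent efficacy control is open to selection bias in either direction; separately, no paired treated-versus-comparator summary is specified

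*Combined protocol and SAP*

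**What the plan says.** The Intervention text, under Prior and Concomitant Medications and Therapies, reads "At least two patches; each measuring 2 cm2 and at least 1 cm from one another will be identified, mapped out, and photographed", followed by "Only one of the alopecic patches will be treated". The Med-Jet procedure in the same list then speaks of injecting patches in the plural.

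Under Clinical Assessments, the Rule of Thumb item names the untreated patch as a comparator: "When selecting the alopecic patch for treatment and its comparator, thumb projections will be used to quantify". What is measured is how much of the scalp hair loss each of the two patches accounts for before treatment. Regrowth from baseline is then graded: "Based on regrowth, the patient will be categorized into one of 6 categories: A0-5". Subjects also rate their "perceived amount of hair regrowth both for the whole scalp and those patches selected at baseline".

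The Data Analysis Plan names AUROC and two optional tests. The chi-square "test may be used for comparison of dichotomous variables", and "the Mann-Whitney test may be used for non-normally distributed continuous variables". It links neither test to an endpoint, a pair of groups or a visit.

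Study Design describes a single intervention with no untreated or needle arm. Efficacy is a secondary objective, and 15 children are to be enrolled.

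**The concern.** The Background section cites spontaneous recovery in an estimated 80% of limited, patchy disease, with no time frame. The exclusion criteria allow existing alopecia treatment unless it began less than 4 weeks before screening. Regrowth from baseline therefore cannot by itself be attributed to the injection. SALT, AA-IGA and whole-scalp ratings do not help, because they mix treated and untreated areas. What can separate a treatment effect from natural regrowth is the comparison of the treated patch with its comparator in the same child.

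That comparison is sound only if the choice of patch is unrelated to how the patches would have fared untreated. If the investigator or family tends to pick the patch likelier to regrow, the contrast favours treatment. If they tend to pick the more stubborn or more visible patch, it may go the other way. Where a child has more than two mapped patches, the choice is wider still.

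The missing contrast is a different problem. It does not bias the control. It leaves the analysis open, and the tests on offer would ignore the pairing.

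**Working it through.** **1. Is there a selection rule?** The relevant sections, side by side:
- Intervention: at least two patches are mapped and one is treated; nothing on how it is chosen.
- Clinical Assessments: thumb projections measure each patch when the pair is selected. This is a measurement, not an allocation rule.
- Study Design, Study Visits and Data Analysis Plan: no mention of random choice, side, size matching, investigator or patient choice, or masking of the rater.

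So no rule is stated.

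**2. Size of the bias from free choice.** The documents give no figure to reproduce: N = 15 rests on pain scores and pilot status, with no SD, effect size or power. The following is an illustration on assumptions:
- no drug effect;
- two patches per child with normally distributed latent regrowth, correlation 0.3, 0.5 or 0.7;
- latent regrowth cut into A0 to A5, either in equal shares or with half in A0 and 10% in each other category;
- the patch that would do better anyway is treated with probability q.

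The expected spurious difference, treated minus comparator, is (2q − 1) × E|D|, where E|D| is the mean absolute difference between the two patches. Over the six settings E|D| runs from about 1.0 to 1.6 categories.

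| q | 2q − 1 | Spurious difference (categories) | Signed-rank significant in the biased direction |
|---|---|---|---|
| 0.3 | −0.4 | about −0.6 to −0.4 | 13–20% |
| 0.4 | −0.2 | about −0.3 to −0.2 | 5–8% |
| 0.5 | 0 | 0 | 1–2% per side |
| 0.6 | 0.2 | about 0.2 to 0.3 | 5–8% |
| 0.7 | 0.4 | about 0.4 to 0.65 | 12–21% |

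The last column is simulated (15 children, 8,000 runs per setting, two-sided 0.05).

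**3. How good must the chooser's cue be?** For one normally distributed cue, its correlation with the between-patch difference must be r = sin(π(q − 0.5)). At q = 0.6 this is sin(0.1π) = 0.31; at q = 0.7 it is sin(0.2π) = 0.59. The documents do not say that size or any other visible feature predicts regrowth, so 70% is best read as an upper illustration.

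**4. Bias against imprecision.** In the same settings, with a true shift of 0 or 0.8 SD, the 95% t-interval half-width at n = 15 is 0.77 to 1.26 categories with pairing and 1.18 to 1.39 without. The 60:40 bias of 0.2 to 0.3 is well inside either.

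**5. Cost of ignoring the pairing.** With random choice and an assumed true shift of 0.8 SD, power is 55–85% for the signed-rank test and 48–51% for Mann-Whitney. Under that analysis this is a loss of precision, not bias.

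**6. A second model for the sign.** Take an assumed 12-week regrowth of 60% in the better patch and 30% in the worse, independent patches, and no drug effect. The expected difference is (2q − 1) × 30 points: +30 if the better patch is always treated, +15 at q = 0.75, 0 at q = 0.5, −15 at q = 0.25 and −30 if the worse is always treated. The exact two-sided McNemar test with 15 pairs rejects in 22.7%, 6.0%, 2.0%, 6.0% and 22.7% of trials. The sign depends entirely on the unstated rule.

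**The case against.** The strongest case on the other side is proportion. This is a 15-child tolerability pilot, efficacy is secondary, and a modest tilt produces a bias smaller than the sampling error. That stands, and it limits the weight of the point. It does not remove it: the analysis can be repaired later, but a free choice of patch cannot be undone once injections begin.

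Four stronger readings are tempting, and the documents do not support them.

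- *The data cannot reveal a biased choice.* They can in part. Patches are mapped and photographed, and each one's share of hair loss is recorded at baseline, so imbalance in size and site can be reported and size adjusted for. Only unmeasured prognosis stays hidden.
- *The plan will analyse patch pairs by Mann-Whitney.* It never says so. That test is optional, is offered for continuous variables, and is tied to no endpoint, while A0 to A5 is ordinal. The power comparison above shows what would be lost if it were used, not what the plan commits to.
- *Randomising the patch makes the contrast unbiased.* It removes selection bias only. The injector and child would be expected to know which patch was injected, and no masking of the rater is described. As an assumption, over-rating the treated patch by one category in 30% of children would add 0.30 × 1 = 0.3 categories in favour of treatment, as much as the upper end of the 60:40 tilt.
- *Patch-level data will be missing because the patient receives the category.* Thumb projections are taken for both patches and patients rate the selected patches. A clarification that each patch is scored is enough.

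**Conclusion.** The point holds as two separate gaps. First, the only concurrent control for the efficacy objective has no stated selection rule, so the treated-versus-comparator contrast can be biased in either direction; a reader might infer bias in favour of the device, but nothing in the documents fixes the sign. Second, no within-child contrast is specified and the only group-comparison tests named are for independent samples, which is an issue of precision and analytic freedom.

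On the assumed inputs, a 60:40 tilt gives about 0.2 to 0.3 spurious categories against a paired half-width of about 0.8 to 1.3. These figures rest on assumed tilt, between-patch correlation and category shares, none of which the documents supply. The primary tolerability objective is not affected, and the efficacy result is descriptive at this sample size. The change should be made because it is cheap and must come before the first injection, not because the trial fails without it.

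**What to change.** - At baseline, map two qualifying patches as A and B and confirm that both meet the eligibility criteria for injection, including exclusion 6 on active infection at the designated site. Only then assign the treated patch from a pre-generated random list, so that exclusions cannot depend on the assignment. If a child has more than two patches, state how the pair is picked.
- Record the A0 to A5 category for each of the two patches.
- Report the within-child difference, treated minus comparator, at Week 12 with a paired confidence interval or signed-rank test, labelled descriptive.
- Report SALT, AA-IGA and whole-scalp ratings as descriptive, noting that they mix treated and untreated areas.
- State that randomisation removes selection bias only and that rating bias in favour of the treated patch may remain. If existing staff can do it, have the existing photographs scored without knowledge of the assignment.
- Reconcile the Intervention statement that one patch is treated with the plural in the Med-Jet procedure. The comparator exists only if one of the pair is left untreated.

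Cost: a short protocol edit, a list of 15 assignments and one extra recorded category per follow-up visit, with no added visits or patients; masked scoring would add some rater time. The downside is that the child and clinician cannot choose which of the two mapped patches is injected.
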